9.2 The Number of Participants

The planned sample size of 2200 patients is based on a high severity pandemic along a range of possible scenarios. This flexibility is important as the accuracy of the modelling may only become clear as the pandemic unfolds.

Based on data from the Department of Health, modelling estimates are that, for a high severity pandemic, 35% of those admitted to hospital will die and 25% will be admitted to intensive care. Of those admitted to intensive care, an estimated 50% will die (estimate derived from UK data related to the 2009 pandemic and to community acquired pneumonia). Thus 47.5% will have the composite outcome of death or admission to hospital in the control group. For this scenario, our study would have 90% power to detect a 15% reduction in relative risk of the composite outcome associated with steroids, and a 20% reduction in deaths. Since a high proportion of those admitted to hospital will die and admissions to intensive care will also be high, therefore, an effect size of 15% would be clinically important.

Table 2 presents a range of scenarios centres around a control event rate of 47.5%.

Control event rate	Relative risk reduction with dexamethasone treatment	N* (80% power)	N* (90% power)
35%	20%	1514	2006
	15%	2704	3592
40%	20%	1242	1644
	15%	2210	2932
47.5%	20%	940	1242
	15%	1662	2204
50%	20%	860	1134
	15%	1514	2010

Table 2: Sample size calculations for a high severity pandemic

* Sample size estimates in each cell have been inflated by 5%, to allow for lack of compliance and loss to follow-up (both anticipated to be low)

For low and moderate severity pandemics, a Hazard Ratio of 1.25, indicating an increased risk of discharge at any given time, is considered as the minimum clinically relevant change to detect. The sample size estimation method is the log rank test allowing for competing risks, and assumes that in the control group 5% are censored at 30 days, and in both groups, 6% (low severity pandemic) and 10% (moderate severity pandemic) die during hospitalisation. With 90% power and 1% two-side alpha, and allowing for 5% non-collection of primary outcome data, a total of 912 and 924 participants are required to be randomised for low and moderate severity pandemics respectively.

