The target sample size for the study is 2200. If the pandemic is of low or moderate severity, it is likely that fewer than 2200 participants will be randomised during the first wave of approximately six weeks duration, although this definition will not be available until after the end of the first wave. If more than 924 participants are randomised in a low/moderate severity pandemic then smaller effect sizes may be detectable.

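### The low/moderate-severity sample sizes of 912 and 924 give about 70% power, not 90%, at a hazard ratio of 1.25 and 1% two-sided alpha

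*Protocol*

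**What the plan says.** Protocol section 9.1 makes time to hospital discharge, censored at 30 days, the primary outcome in a low- or moderate-severity pandemic. Section 9.2 gives the sample size for that outcome.

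- Effect: "a Hazard Ratio of 1.25, indicating an increased risk of discharge at any given time", described there as the smallest clinically relevant change.
- Method: "The sample size estimation method is the log rank test allowing for competing risks".
- Losses: the calculation "assumes that in the control group 5% are censored at 30 days". Deaths before discharge are put at 6% of each arm for low and 10% for moderate severity.
- Result: "With 90% power and 1% two-side alpha, and allowing for 5% non-collection of primary outcome data, a total of 912 and 924 participants" for low and moderate severity respectively.

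Section 9.2 then uses the larger figure as a benchmark: "If more than 924 participants are randomised in a low/moderate severity pandemic then smaller effect sizes may be detectable".

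**The concern.** In a log-rank test, power depends on the number of events, and each patient can contribute at most one discharge. A hazard ratio of 1.25 is a modest effect and 1% two-sided alpha is strict, so the event requirement is large. A total of just over 900 randomised looked too small to meet it.

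Section 9.2 expects that fewer than 2,200 will probably be randomised in the first wave of a low/moderate pandemic. Section 6.1 has the final sample size set with the Trial Steering Committee during activation. A committee working quickly could take 924 as enough for 90% power at a hazard ratio of 1.25. If recruitment ended near there, the chance of missing a true effect of that size would be about 30%, not 10%, and a null result would look more informative than it is.

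**Working it through.** **Inputs (Protocol section 9.2).** Hazard ratio 1.25; two-sided alpha 0.01; power 0.90; 5% of controls censored at 30 days; in-hospital deaths 6% (low) or 10% (moderate); 5% of outcomes not collected; totals 912 and 924. Two assumptions are added: 1:1 allocation (the protocol gives no ratio, and unequal allocation would only lower power) and, for the central estimate, constant cause-specific hazards.

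**Step 1: events required.**

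- Schoenfeld: d = 4(z₀.₉₉₅ + z₀.₉₀)² / (ln 1.25)² = 4 × (2.576 + 1.282)² / 0.2231² = 4 × 14.88 / 0.0498 = 1,195.3, so 1,196.
- Freedman: d = 14.88 × (2.25/0.25)² = 14.88 × 81 = 1,205.2, so 1,206.

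Both exceed 912 and 924. The stated figures therefore fail whatever is assumed about censoring or competing deaths.

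**Step 2: best-case power.** Power = Φ(√(d/4) × 0.2231 − 2.576).

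- Every randomised patient has an observed discharge: d = 912 gives Φ(0.79) = 79%; d = 924 gives Φ(0.82) = 79%.
- Every patient with a collected outcome is discharged (0.95 × 912 = 866; 0.95 × 924 = 878): 76% and 77%.

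**Step 3: power with the protocol's own losses.**

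| | Low | Moderate |
|---|---|---|
| Control discharged (1 − 0.05 − deaths) | 0.890 | 0.850 |
| Dexamethasone discharged (discharge hazard × 1.25) | 0.925 | 0.891 |
| Mean | 0.908 | 0.870 |
| Expected discharges (N × 0.95 × mean) | 786 | 764 |
| Power, 1% two-sided | 71% | 69% |
| Power, 5% two-sided | 88% | 87% |

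Other ways of handling the competing deaths were also tried: the same discharge probability in both arms, the death percentage held fixed in both arms, and a subdistribution hazard ratio. With either formula, power is 70% to 71% for 912 and 68% to 70% for 924. A simulated cause-specific log-rank test (4,000 replicates) gave 71% for both.

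**Step 4: what 90% power needs.**

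- 1% alpha: 1,196 / (0.908 × 0.95) = about 1,387 (low); 1,196 / (0.870 × 0.95) = about 1,447 (moderate). Across the variants the ranges are about 1,380 to 1,430 and 1,430 to 1,495.
- Hazard ratio detectable at 912 or 924 with 90% power and 1% alpha: about 1.32.

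**Step 5: can 912 and 924 be reproduced?** Not at 1% alpha by any standard variant. One-sided 1% alpha gives power of only 77% to 79%. Dropping to 80% power at two-sided 1% still needs about 1,083 to 1,172. At 5% two-sided alpha, 845 discharges are required, so the totals are 845 / (0.908 × 0.95) = about 980 and 845 / (0.870 × 0.95) = about 1,022, still above the stated figures. The nearest match is 5% alpha with deaths ignored: mean discharge probability 0.963, and 845 / 0.963 / 0.95 = 924. That uses neither the stated alpha nor the stated deaths.

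For comparison, the 16 cells of Table 2 (high severity) all reproduce to within about 2 participants at 5% two-sided alpha, with continuity correction and division by 0.95. The cell for a 47.5% control rate, 15% reduction and 90% power comes out at 2,202 against 2,204 printed. At 1% alpha it would be 3,095.

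**The case against.** The arithmetic in Step 1 has no good answer, but several points limit its weight.

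- **No stopping rule at 924.** The target stays at 2,200, and severity will be defined only after the first wave. If 2,200 were recruited, the same method gives 0.95 × 2,200 × 0.908 = 1,898 or 0.95 × 2,200 × 0.870 = 1,818 discharges, and power of about 98% to 99% at 1% alpha. The shortfall matters only if recruitment ends below roughly 1,390 to 1,450. This stands, but section 9.2 itself expects fewer than 2,200 in these scenarios and offers 924 as the benchmark.
- **Results come with 95% confidence intervals** (section 9.1), so a reader can see what a null result excludes. This is true, and it softens the risk of over-reading, but it does not make the power statement right.
- **Different alphas are allowed.** The protocol states no alpha for Table 2, and two scenarios with different primary outcomes may use different levels. That is fair: the difference is not an error in itself.
- **The source of the slip is unknown.** It could lie in alpha, power, hazard ratio or N. The near match at 5% alpha is only an inference, and ignoring deaths it fits 924, the figure for the scenario with more deaths.

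A separate statistical analysis plan may hold the original calculation, but it cannot make the inputs and output printed here compatible.

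**Conclusion.** The statement is wrong as written. With a hazard ratio of 1.25 and 1% two-sided alpha, 912 and 924 participants give about 70% power (68% to 71% across models), some 20 percentage points below the 90% claimed. The required totals are about 50% larger than stated. That 90% cannot be reached follows from the event count alone and needs no modelling assumption. The 70% rests on the protocol's own loss figures and 1:1 allocation, and it barely moves with the treatment of competing deaths. The replacement totals are somewhat more sensitive and are best given as ranges. The practical consequence is conditional on recruitment ending well short of 2,200, which the protocol regards as likely in these scenarios.

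**What to change.** Retrieve the original calculation and make alpha, power, hazard ratio and N agree in section 9.2. Three consistent versions are:

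- keep 912 and 924 and restate power at a hazard ratio of 1.25 as about 71% and 69% at 1% alpha (about 88% and 87% if 5% was intended);
- keep 90% power, 1% alpha and a hazard ratio of 1.25, and restate the totals as about 1,390 (1,380 to 1,430) for low and 1,450 (1,430 to 1,495) for moderate severity;
- keep 912 and 924 with 90% power at 1% alpha, and state the detectable hazard ratio as about 1.32, acknowledging that this is larger than the minimum effect the protocol calls clinically relevant.

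Replace the 924 in the paragraph that follows with whichever figure results. State the hazard model and allocation ratio used. It would also help to print the alpha behind Table 2 and confirm whether 1% is intended for the low/moderate case; using one alpha for both is optional.

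The cost is wording in the protocol, and in the statistical analysis plan if the figures are repeated there. The 2,200 target, the outcomes and the procedures do not change, but a published power or sample size figure becomes less favourable.

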9.3 Interim Analyses

The objective of the trial is to complete recruitment within the first pandemic wave. Typically, a pandemic wave is of 6 weeks' duration. Therefore, it is expected that there will be insufficient time to perform a meaningful interim analysis based on efficacy data prior to close of recruitment. An early analysis will be

conducted at the close of recruitment and before the second pandemic wave. Given the timeframes involved, this early analysis will report on the primary outcome and as many other outcomes as possible.

9.4 **Procedure for accounting for missing, unused, and spurious data.**

The reason for missing data will be checked. Sensitivity analysis will be performed prior to imputation of missing data. If imputation is required, multiple imputation will be considered if data missing are at random. Otherwise, a selection bias collection model within a mixture model framework will be considered.

Both missing data and spurious data will be queried.

10 DIRECT ACCESS TO SOURCE DATA/DOCUMENTS

Direct access will be granted to authorised representatives from the sponsor, NCTU, host institution and the regulatory authorities to permit trial-related monitoring, audits and inspections.

11 QUALITY CONTROL AND QUALITY ASSURANCE PROCEDURES

The study will be conducted in accordance with the current approved protocol, ICH GCP, relevant regulations and standard operating procedures.

Data will be evaluated for compliance with the protocol and accuracy in relation to source documents. Following written standard operating procedures, the monitors will verify that the clinical trial is conducted and data are generated, documented and reported in compliance with the protocol, GCP and the applicable regulatory requirements.

A Trial Steering Committee (TSC) has been established which includes an independent chair, two independent members and patient representatives. The TSC will meet to discuss and agree the final protocol version, and it will approve the Statistical Analysis Plan before the trial data are unblinded.

The TSC have agreed to meet (either in person or by telephone) every three years during the hibernation phase. A yearly report will be produced by the TMG and sent to the TSC. Should any of the information contained in the report warrant a meeting this will be arranged.

The TSC will be responsible for activating the trial in consultation with the TMG, NIHR and Department of Health.

An independent Data Monitoring Committee (DMC) will be established and will act in accordance with the pre-agreed terms of reference. Only the DMC will have access to unblinded data until the final assessment has been completed.

The Trial Management Group (TMG) will be responsible for day-to-day supervision of the study. Membership will include the CI, the trial manager and at least one other member of the NCTU. The TMG will be responsible for ensuring project milestones are achieved. The TMG will meet monthly during the set up phase, 6 monthly during the 'hibernation' phase, and every 2 to 8 weeks during the activation phase (depending on need). The TMG will report at least annually to the TSC.

Recruitment rates at sub-study sites will be monitored closely by the Trial Management Group TMG and TSC.

12 ETHICS

12.1 Declaration of Helsinki

The Investigator will ensure that this study is conducted in full conformity with the current revision of the Declaration of Helsinki (last amended October 2000, with additional footnotes added 2002 and 2004).

12.2 ICH Guidelines for Good Clinical Practice

The Investigator will ensure that this study is conducted in full conformity with relevant regulations and with the ICH Guidelines for Good Clinical Practice (CPMP/ICH/135/95) July 1996.

12.3 Approvals

Trial documents including the protocol, consent documentation, participant information sheet, postal questionnaire and any proposed advertising material will be submitted to an appropriate Research Ethics Committee (REC). Required documents will also be submitted to the regulatory authorities (MHRA in the UK), and host institution(s) for written approval.

The Investigator will submit and, where necessary, obtain approval from the above parties for all substantial amendments to the original approved documents.

12.4 Participant Confidentiality

The trial staff will ensure that the participants' anonymity is maintained. Each participant will be assigned a Participant ID number, allocated at randomisation, for use on trial documents and the trial database. The documents and database will also use the patient's initials. The patient's date of birth will also be entered into the database.

The participants will be identified only by participant ID number on the trial database and on the follow-up questionnaire returned to the NCTU. All documents will be stored securely and only accessible by trial staff and authorised personnel. The study will comply with the Data Protection Act.

12.5 Other Ethical Considerations

There are no additional ethical considerations.

13 DATA HANDLING AND RECORD KEEPING

All trial data will be entered onto a trial specific macro system, via a secure web browser session. Access to the system will be restricted and secure using password protection. All data will be stored on a secure server. Access will be restricted by user identifiers and passwords.

Electronic data will be backed up every 24 hours to a remote secure encrypted server.

For the follow up questionnaire and registration of participants with the HSCIC, identifiable information about participants will be held in a separate area of the system. Access to this information will be restricted to those involved in the follow up phase, as authorised by the Chief Investigator. Only the participant number will be used on the follow up questionnaire that will be posted back to NCTU.

14 FINANCING AND INSURANCE

This study is funded through the NIHR Programme NETSCC Pandemic Flu personal award (11/46/14). Nottingham University hospitals NHS Trust will act as the main sponsor for this trial. Delegated responsibilities will be assigned to the NHS trusts taking part in this trial. Standard NHS Indemnity applies.

15 PUBLICATION POLICY

The study has been designed and will be reported according to the CONSORT guidelines. The findings from this study will provide robust evidence for clinicians working in acute medical services including Emergency Departments. Findings will be published in peer-reviewed scientific journals, medical society newsletters and where possible in the local press and media. The results will be presented at national and

international conferences. Participants who requested a copy of the report will be sent a lay summary of the study

16 HEALTH ECONOMICS

A provider perspective for costs will be adopted. For patients in both the test and the control arms, management will entail up to 4 different episodes of hospital stays, plus primary care visits following discharge. The cost for each patient is therefore the sum of the following (where IP = inpatient, LOS = length of stay, in days).

- Cost of initial IP admission = cost of IP stay per diem * LOS1.
- Cost of readmission = cost of IP stay per diem * LOS2.
- Cost of intensive/critical care = cost of ICU per hour * LOS3 * 24
- Cost of intervention-related complications = cost of IP stay per diem * LOS4.
- Primary care costs = cost per GP consultation * number of condition-related consultations.

The trial will record the 4 types of IP LOS and GP visits for each patient, enabling calculation of patient specific health system costs (following multiplication by the appropriate units costs).

For patients admitted to critical care, separate national tariffs for critical care which have been developed in relation to the number of organs supported (zero to six, reference costs currency codes XC07Z to XC01Z) will be used to attribute critical care costs weighted by degree of support to each subject under treatment.

From a health outcome point of view, the only difference between the trial arms will be in their death rates. Given the age at death for each patient, the expected total and average life years lost in each arm using conventional life-tables will be calculated.

The results will be expressed as the:

- Average management cost per patient for each arm.
- Incremental cost-effectiveness ratio (mean cost per life year gained, test arm relative to control).

APPENDIX A – TRIAL FLOW CHART

APPENDIX B – MECHANISTIC SUB-STUDY: DETERMINING THE INTERACTION OF STEROID THERAPY AND THE HOST

PLEASE NOTE THAT THIS SUB-STUDY WILL ONLY BE CONDUCTED AT THE FOLLOWING SITES:

- 1) Aintree University Hospital, Liverpool
- 2) City Hospital, Nottingham
- 3) Manchester Royal Infirmary
- 4) Queen's M edical Centre, Nottingha m
- 5) Royal Liverpool University Hospital
- 6) Southampton General Hospital

IMPORTANT: THIS APPENDIX IS ONLY APPLICABLE TO THE ABOVE LISTED SITES.

Aims

This mechanistic sub-study aims to address the following key questions in the treatment of influenza:

- a) For each patient, what was the point in the natural history of influenza infection at which admission occurred?
- b) What effect dose steroid have on the natural history of influenza infection defined by clinical phenotype and RNA transcriptomic pattern?
- c) Does comparison of the transcriptomic pattern in placebo versus steroid treated arm suggest proinflammatory and anti-inflammatory mechanisms are both altered?

Background

The NIHR have recommended that a mechanistic sub-study be conducted as part of the ASAP trial. This sub-study will be conducted in a limited number of pre-selected ASAP trial sites. These sites have been selected as they are considered to have sufficient staff and infrastructural capacity to manage the additional work related to the sub-study without compromise to clinical care delivery or conduct of the main ASAP trial.

The onset of symptoms is highly variable in influenza exposed adults¹ and the severity of symptoms is the result of a complex host-pathogen interaction² altered by co-infection and co-morbid illness³. Initially, cytokine data were used to describe this interaction, but recent data from a unique human influenza challenge study have fully described the human inflammatory and anti-inflammatory pathways that determine symptom severity in exposed adults⁴. Using whole genome arrays (Affymetrix Human Genome U133A v2), 5076 genes showed altered expression during the 5 days following influenza A exposure. Unsupervised and clinically informed analyses resulted in self-organising maps (clustered gene expression patterns) which showed 8 functionally important gene sets in which activation/inhibition was tightly associated with clinical severity (see reference 4). The study also described the duration in hours between virus exposure and significant difference in self-organising map (SOM) cluster expression between symptomatic/asymptomatic subjects.

Thus, this sub-study will apply the best contemporary (with respect to the time of pandemic declaration) methods to a representative sample (n=200) of ASAP trial participants in order to determine the interaction of steroid therapy and the host and to apply this in interpreting the clinical outcome measured.

[figure not shown]
Methods/Design

Patients recruited into the ASAP trial at the sub-study sites will be given the opportunity to participate in the sub-study. 200 patients who have received ASAP study medication are required for the sub-study.

ASAP trial participants who consent to participation in the sub-study will give two blood samples and have one nasal swab taken for subsequent transcriptomic and microbiological testing. Blood samples will be collected into vaccutainer tubes at baseline and 48 hours post first dose of ASAP study medication. These time points are practical and match the best available transcriptomic data and the expected time course of steroid effect on gene expression. These samples can be collected using standard venesection methods and transferred without urgency to frozen storage in the hospital clinical laboratories. These sample collections should therefore be minimally obstructive in the context of a pandemic. The nasal swab for virological confirmation will be obtained at the time of the first blood sample collection. Please see figure 1 for an overview of the sub-study design.

The overarching principle in relation to the conduct of the mechanistic sub-study is that it should not disadvantage or jeopardise conduct of or recruitment into the main ASAP trial. Six sites have been selected to participate in the sub-study and the decision to activate the sub-study and these sites will be determined by the Trial Management Group according to pre-agreed criteria. The ability of these sites to conduct the sub-study will continue to be monitored by the Trial Management Group throughout the recruitment phase.

Figure 1: Overview of the sub-study design

* Blood and nasal samples are required at the latest 4 hours after first dose of study medication so consent must

have been obtained prior to the samples being taken.

[#] Sample should be obtained at 48 hours (+/- 3 hours) or at discharge if this is sooner

Participants and recruitment

All patients recruited into the ASAP trial at sub-study sites will be eligible to participate in the sub-study.

In order to fulfil the sampling requirements, recruitment into the sub-study should only be considered where it is practically possible to obtain consent for the sub-study and take the first blood sample required for the sub-study either before the participant receives their first dose of ASAP study medication or within 4 hours of the first dose of ASAP study medication being administered.

ASAP trial participants will be approached by a doctor or nurse following consent into the ASAP trial, either at the point of recruitment into the ASAP trial or shortly after being recruited into the ASAP trial.

Consent must be obtained for all patients recruited into the sub-study in a similar manner as for the ASAP trial to ensure a representative sample of participants.

A separate sub-study patient information sheet and consent form will be used.

The procedure for obtaining consent for the sub-study is as follows:

Patients with capacity to consent (non-emergency situation)

ASAP trial participants will be provided with a sub-study patient information sheet and a doctor or nurse will give a verbal explanation of the study. It will be clearly stated that the patient is free to withdraw from the sub-study at any time and for any reason without affecting their future care, and with no obligation to give the reason for withdrawal. The ASAP trial participant will be given the opportunity to ask any questions and if they agree to participate in the sub-study they will be asked to sign a consent form. The participant must personally sign and date the latest approved version of the informed consent form before any sub-study procedures are performed. The person obtaining consent must be suitably qualified and experienced, and have been authorised to do so by the ASAP Trial Principal Investigator.

Once written consent has been obtained, the patient will be enrolled onto the sub-study.

Patients with capacity to consent (emergency situation)

In the same manner described in the ASAP trial protocol, where a patient has capacity to consent but is in an emergency situation whereby it is not medically appropriate to delay the start of the ASAP study treatment, one **independent doctor** should consider the patient's eligibility criteria and any known views of the patient about participation and decide whether or not to enrol the patient into the sub-study.

Once the decision has been made to enter the patient into the sub-study this must be documented by the clinician in the patient's medical notes. The participant may then be enrolled into the sub-study. Written consent must be sought later.

Patients without capacity to consent

If, in accordance with the ASAP trial protocol a patient is judged to lack capacity to consent, one **independent doctor** should consider the patient's eligibility criteria and any known views of the patient about participation and decide whether or not to enrol the patient into the sub-study.

Once the decision has been made to enter the patient into the sub-study this must be documented by the clinician in the patient's medical notes. The participant may then be enrolled into the sub-study. Written consent must be sought later.

Written consent for patients that lacked capacity at enrolment and emergency situations

For patients who lack capacity to consent at enrolment or patients with capacity that are entered into the trial under emergency situation regulations, written consent must be obtained by a doctor or an appropriately trained nurse from the participant (if capacity has been recovered) or Personal Legal Representative as soon as it is practicable to do so.

A Personal Legal Representative may be a partner, friend or relative.

The participant's decision to withdraw from the sub-study would overrule any decision made by a doctor or Personal Legal Representative.

Sampling requirements

Sub-study participants will give two blood samples and a nasal swab for sub-study purposes. All samples will be obtained by an appropriately trained doctor or nurse.

Table 1 provides a summary of the samples required.

Table 1: Sub-study samp le requirement s

Time point	Sample	Details	
	16 ml peripheral blood	2 x 2.5 PAXgene tubes (RNA expression analysis)	
Baseline		1 x 6ml plasma gel tube (corticosteroid pharmacokinetics)	
(after recruitment into ASAP trial and before, or within 4 hours of 1 st dose of ASAP		1 x 5ml serum gel tube (multiplex cytokine array)	
study medication)	Nasal swab	Collected in standard viral transport medium. This sample will be in addition to any nasal swab taken for clinical purposes, but may be taken at the same time-point if appropriate.	
Mid-treatment	20 ml peripheral blood	1 x 5ml plasma gel tube (corticosteroid pharmacokinetics)	
(48 hours (+/- 3 hours) after 1 st dose of study medication, or prior to hospital discharge,		1 x 5ml serum gel tube (multiplex cytokine array)	
whichever is sooner)		1 x 10ml EDTA tube (genotyping)	

Sample collection, storage and transport

Blood samples

A 16ml peripheral blood sample must be obtained before or within 4 hours of the first dose of ASAP study medication being given to the participant. Blood will be collected into 3 different tube types as outlined in Table 1. Of note, the PAXgene tubes should be collected last and should be used along with an extension adapter. Use of the adapter reduces the risk of reflux of the PAXgene preservative liquid during the blood draw.

A second 20ml peripheral blood sample must be obtained mid-treatment (at 48 hours (+/- 3 hours) after the first dose of ASAP study medication, or prior to hospital discharge, whichever is sooner).

Blood samples will be labelled with a unique sample identifier which will encode the study, participant trial ID number and the sample type and time point. All blood samples will be sent to the clinical laboratories at the hospital where the participant has been recruited. PAXgene tubes must stand at room temperature (RT) for at least 3 hours and no longer than 72 hours. They are then transferred to a standard -21°C freezer then when frozen racked and transferred to a -80°C freezer. The initial RT phase enables the RNA stabilisation solution to penetrate cells. The -21°C freeze prevents the glass bottle cracking when taken down to -80°C. Serum gel and plasma gel tubes will be labelled with similar unique identifiers. They should be spun and separated into 500uL aliquots which should be labelled, racked and frozen at -80°C.

All blood samples should be retained at site until recruitment to the sub-study has been completed. Frozen blood samples should then be sent by courier, on dry ice in a single batch to the Liverpool School of Tropical Medicine (LSTM) where they will be stored at -80°C until analysed. A Material Transfer Agreement (MTA) will be established between recruiting sites and LSTM to facilitate this.

Nasal swabs

A nasal swab must be taken on enrolment. Standard virus swabs with associated virological media will be used and provided in study packs to participating sites by the coordinating centre in Liverpool. All swabs will be promptly labelled and frozen to -80°C. All swabs will subsequently be transferred on dry ice to the Department of Virology, Royal Liverpool University Hospital where then will stored until analysis is performed.

Equipment for sampling

All materials related to the mechanistic sub study samples will be purchased by, and packs created in, Liverpool. These study packs will then be sent out to the sub-study sites.

Sample analysis

Blood samples

Once blood samples are received at the Liverpool School of Tropical Medicine, HTA compliant storage and archiving (Procuro system used for laboratory information) of blood samples will be provided in the Liverpool School of Tropical Medicine Respiratory Infection group.

Analysis of samples will be performed in a single batch using either RNA microarray expression analysis or next generation sequencing, depending on which is the most cost-effective method to obtain the data needed at the time analysis is carried out. This is a fast-moving technology and while the current balance would still favour microarray, it is anticipated that this will no longer be the case in a few years.

An inflammatory array of genes expressed during acute influenza (+/- steroids) will be described (using microarray or sequencing technology). These data will inform the clinical severity score, the duration of illness and most importantly will confirm the immune-modulatory effect of steroids

Nasal swabs

The latest test available to detect influenza virus including the pandemic strain will be used; this is expected to be a PCR test, however the specific test cannot be determined until the point of trial activation. After testing, all nasal swabs will be disposed of.

Surplus samples

Consent will be sought from sub-study participants for any remaining samples to be stored and used for future ethically approved research. Where consent has been given remaining samples will be stored in under a storage license from the Human Tissue Authority (HTA). Request for access to these samples for future ethically approved research will be made through the Chief Investigator and lead sub-study Investigator. Any outputs arising from use of these samples must reflect the contributions of both study teams.

Data collection

No additional data over and above that collection for the ASAP trial is required for the sub-study.

Withdrawal

Each sub-study participant has the right to withdraw from the sub-study at any time. In addition, the investigator may withdraw a participant from the sub-study at any time if the investigator considers it necessary for any reason. Any samples already collected for the sub-study would still be used unless specifically requested not to, in which case any samples collected would be destroyed.

The reason for withdrawal from the sub-study will be requested and recorded in the trial database, however participants are not obliged to give reasons.

There will be no replacement of participants who withdraw from the sub-study.

Statistical analyses

Data arising from the sub-study will be analysed by sub-study investigators at the Liverpool School of Tropical Medicine and University Hospital Aintree.

The following assumes that the platform chosen to achieve the stated aims is microarray analysis of the whole blood RNA transcriptome between subjects (placebo vs control) normalised to the transciptome of a set of healthy volunteers.

All analyses will be conducted in the latest version of R (currently 3.1.0). For analysis of the RNA transcriptome data we will use the latest version of the package Bioconductor (currently version 2.14). An initial normalisation step will be carried out to account for technical variation in the gene expression data between samples. Differential gene expression analysis will be explored between treatment and control samples using the normalised expression data.

- To address aim one, using day zero data, levels of expression of genes that defined temporal stage in the paper by Huang et al. will be summarised using appropriate descriptive statistics in order to define when in the course of flu infection patients were recruited to the study.
- To address aim two comparing steroid with placebo groups, between-group differences in the expression of relevant genes on day 3 will be estimated using appropriate regression models 4.
- To address aim three functional analysis of genes of interest (those that are differentially expressed between treatment and placebo groups) will be performed to infer the mechanism of action of steroid when given to patients with pandemic influenza; this will be a descriptive analysis.

References

- 1 F. Carrat, E. Vergu, N. M. Ferguson, M. Lemaitre, S. Cauchemez, S. Leach, and A. J. Valleron, 'Time Lines of Infection and Disease in Human Influenza: A Review of Volunteer Challenge Studies', *Am J Epidemiol*, 167 (2008), 775-85.
- 2 M. D. de Jong, C. P. Simmons, T. T. Thanh, V. M. Hien, G. J. Smith, T. N. Chau, D. M. Hoang, N. V. Chau, T. H. Khanh, V. C. Dong, P. T. Qui, B. V. Cam, Q. Ha do, Y. Guan, J. S. Peiris, N. T. Chinh, T. T. Hien, and J. Farrar, 'Fatal Outcome of Human Influenza a (H5n1) Is Associated with High Viral Load and Hypercytokinemia', *Nat Med*, 12 (2006), 1203-7.
- 3 M. B. Rothberg, and S. D. Haessler, 'Complications of Seasonal and Pandemic Influenza', *Crit Care Med*, 38 (2010), e91-7.
